Individuals recruited from MGB sources may have medical records reviewed for eligibility. In order to assess eligibility of all individuals, we may ask pre-screening questions via telephone or REDCap, and may request clinical notes and/or endocrine labs from their Endocrinologist, PCP, or other health care provider. If outside records are requested, candidates will be asked to complete medical record release forms. Identifiable information on individuals who do not enroll may be retained but will not be linked to any collected health information without permission of the individual.

Consent Process

Consent may be obtained either in-person (at Massachusetts General Hospital) or remotely. The consent form is provided for the subject to review prior to the consent process and study participation. Informed consent will be obtained by a licensed physician investigator or by non-physician investigators who are nurse practitioners or physician assistants with backup by a licensed physician.

The consent process will take place prior to the commencement of study procedures and will, in all instances, include a complete explanation of the study by one of the study medical professionals (physicians, physician assistants, or nurse practitioners). Study staff will go over the purpose of the study, study procedures, potential risks of participation, and alternatives to participation. Before signing an approved consent form, potential participants will be given the opportunity to ask any questions that they may have concerning the study. The voluntary nature of participation in these studies will be emphasized. It will be made clear that a decision not to participate will in no way affect the relationship of patient to medical professional, investigator, or institution regarding the ongoing provision of care.

When consent is obtained in-person, the subject will sign the consent form in the presence of the study medical professional after all parts of the consent process are completed. The study medical professional will also sign the consent form at the time of the visit as well.

When consent is obtained remotely, the study investigator will complete the consent process, as described above, over the phone. The study investigator will confirm subject's identity before signature is obtained. The subject and study medical professional will sign the consent form at this time.

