- If applicable, remote screening laboratory studies will be performed at a local laboratory site (e.g., Quest Diagnostics, etc.); study funds will pay for all phlebotomy and shipping costs.

If all eligibility criteria are met, a member of the study team will contact the subject to schedule the study visits.

2. Pre-Study Visit Interventions

Sex-steroid and Medication Discontinuation (“washout”)

Subjects on hormonal medication (including oral contraceptives or hormone replacement) or non-hormonal medication that may modulate the reproductive axis may be asked to undergo a washout period appropriate to that particular medication and its method of administration as follows:

- Pulsatile GnRH therapy > 2 weeks
- Gonadotropin injections > 4 weeks
- Transdermal testosterone > 2 weeks
- Testosterone injections > 6 weeks
- If not specified above, a length of time > 5 half-lives of the drug

Subjects will be advised to discuss the washout with their prescribing physician prior to beginning washout. Any subject who experiences intolerable side effects as a result of medication washout will end participation in the study and be instructed to follow recommendations by their prescribing physician regarding resuming any medications. Subjects will be advised to consult with their prescribing physician to reinstate any medications after the study visit is complete.

Any active use of marijuana will be evaluated by a study medical professional to determine if it may impact study participation. Individuals who regularly use marijuana will be asked to abstain from use for two weeks prior to the study visit. ³⁰

3. Study Visit

Frequent blood sampling will be performed over 3 hours. The first 1.5 hours will assess the intrinsic activity of the reproductive axis (baseline), and the second 1.5-hour period will show the response to a naloxone bolus. The study visit may occur at the MGH Translational and Clinical Research Centers (TCRC) or at the Reproductive Endocrine Unit.

All visits will adhere to the following protocol:

- To ensure that measured testosterone values are accurate, male participants will be asked to fast overnight (at least 8 hours) and to remain fasted during the entirety of the study visit.
- Frequent blood sampling: blood will be drawn q10 minutes for three hours.

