Power calculation: Informed by the difference in mean LH levels in healthy men and women observed before and during naloxone infusion, we calculate that a sample size of 8 subjects would provide 90% power to detect a significant difference in mean LH before and after the naloxone bolus.

VII. RISKS AND DISCOMFORTS

The risks involved with this study are associated with the administration of study drug and frequent blood sampling.

Blood Draws and IV Sites:

There may be discomfort and/or pain associated with the placement of IV lines and a small risk of infection, bruising, thrombosis, and irritation at blood draw sites, including at sites of IV line placement. There is a slight chance that an IV line placed will fail. In the event this occurs, a new IV line will be placed. Participants might experience dizziness or faint in association with the placement of and blood drawing from IVs. IVs are generally covered/stabilized with some form of adhesive tape or dressing during the study visit. Participants might experience temporary skin irritation or discomfort from these adhesive products.

EMLA Cream

Repeated doses of EMLA Cream may increase blood levels of lidocaine and prilocaine, although systemic adverse reactions following appropriate use of EMLA Cream are unlikely due to the small dose absorbed. There have been reports of slight reddening, swelling, discoloration, rashes,

and hyperpigmentation at the application site, but these cases were generally mild and transient. No serious reactions have been reported.

Naloxone:

Naloxone has no known side effects in healthy adults. In opioid-dependent individuals, naloxone may produce symptoms of acute opioid withdrawal such as pain, agitation, diaphoresis, and hypertension. To prevent such a reaction, all subjects will be screened and excluded for evidence of illicit drug use. Subjects will be closely monitored after the naloxone bolus.

Medication Washout

Subjects who discontinue the use of their current medications may experience the return of symptoms that are controlled or mitigated by these medications. However, we do not expect our participants to experience a prolonged recurrence of symptoms, and we expect any short-term symptoms to be rapidly reversible. Subjects who experience intolerable side effects as a result of medication washout will end participation in the study.

VIII. POTENTIAL BENEFITS

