There are no direct benefits to subjects that are anticipated from participating in this study. The only benefit comes from the altruistic contribution to furthering our understanding of the biology of human reproduction.

IX. MONITORING AND QUALITY ASSURANCEAdverse Event (AE) Documentation/Review:

The terminology from NCI Common Terminology Criteria for Adverse Events (CTCAE) v5.0 will be utilized for AE documentation. AEs that occur from enrollment (signing of consent form) until the end of study procedures will be recorded.

In addition to contemporaneous documentation and review of AEs by the Study Investigators as they occur, PI-initiated safety monitoring formally occurs at recurring quarterly internal meetings (4 or more times per year), when AEs are reviewed by the PI and multiple study Co-Investigators.

Adverse Event (AE) Reporting:

The Principal Investigator will report adverse events to the MGB IRB in accordance with MGB IRB guidelines.

Unanticipated Problem Reporting:

As per MGB IRB guidelines, the Investigator will report Any Unanticipated Problem Involving Risks to Subjects or Others (including related, unanticipated, Serious Adverse Events) to the MGB IRB by telephone, fax, or email within 5 working days/7 calendar days of becoming aware of the problem.

Monitoring:

The Principal Investigator is responsible for oversight of the trial. Clinical research coordinators and program managers regularly monitor collected source data and regulatory documentation for accuracy and completeness. All protocol deviations are documented and reported in accordance with MGB IRB guidelines. The PI will conduct interim monitoring of accumulated data from research activities to assure the continuing safety of participants, relevance of the research

question, appropriateness of the study design and statistical analysis, and integrity of the accumulating data.

The study will also be monitored by an independent Data Safety Monitoring Board.

The DSMB responsibilities will include:

- Review of the research protocol, informed consent documents and plans for safety and data monitoring of the study. This is to determine the risks and benefits to research subjects, protection and safety of the subjects and to offer suggestions for improving the study design.

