- Review of all adverse events (expected, unexpected and serious), enrollment, and dropout rates and protocol deviations. This is conducted to ensure subject safety. The Board will be provided with reports of serious adverse events as they occur and may request additional information from the Investigator in the course of its review.
- Evaluation of the progress of the trial, including periodic assessments of data quality/completeness, recruitment goals, protocol adherence, accrual and retention of participants and other factors that may affect the study outcome. Protect confidentiality of the study participants, trial data and results of the monitoring.
- Weighing efficacy and adverse events to determine if the trial should continue as originally designed, should be changed or should be stopped based on the data.

A copy of the minutes will be distributed to the DSMB members, the Principal Investigator and the IRB. The minutes will reflect which of the following three determinations the DSMB may make as a result of its review: 1) the study may continue without modification/amendment; 2) the study should be amended; 3) the study should terminate.

Reference List

5. Young J, Bouligand Jm, Francou B, et al. TAC3 and TACR3 defects cause hypothalamic congenital hypogonadotropic hypogonadism in humans. *The Journal of Clinical Endocrinology & Metabolism* 2010;95(5):2287-2295.

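### Adverse-event recording stops when study procedures end and no post-visit contact is planned, so late IV-site events and some washout symptoms may go unrecorded

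*Combined protocol and SAP*

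**What the plan says.** Section IX (Adverse Event Documentation/Review) sets the recording window: "AEs that occur from enrollment (signing of consent form) until the end of study procedures will be recorded". It does not define when procedures end.

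The window opens early. Under Consent Process in Section IV, "The consent process will take place prior to the commencement of study procedures". Section V then places screening, any medication washout and the study visit in that order. The visit is arranged only after screening: "If all eligibility criteria are met, a member of the study team will contact the subject to schedule the study visits".

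The visit is the last procedure described. It has 3 hours of sampling, with the bolus dividing two 1.5-hour periods. Follow-up beyond it is mentioned only for a participant who develops high blood pressure or an allergic reaction.

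Section VII lists "a small risk of infection, bruising, thrombosis, and irritation at blood draw sites". It also says that participants who stop medication "may experience the return of symptoms that are controlled or mitigated by these medications". On restarting, Section V.2 says: "Subjects will be advised to consult with their prescribing physician to reinstate any medications after the study visit is complete".

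The monitoring board's duties in Section IX begin with the protocol and safety plans and go on to "Review of all adverse events (expected, unexpected and serious").

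**The concern.** The recording rule and the risk list do not fully match. Two listed harms, infection and thrombosis at a cannula site, need not show themselves before the participant goes home. Washout exposure also continues past the visit, because medication is restarted only afterwards and through the prescriber. An event that starts in either period falls after the cut-off, and no planned contact would bring it to the team's attention.

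The board is asked to review every adverse event, but it can review only what is recorded or otherwise reported. If no late events were listed, a reader could not tell whether none occurred or none were looked for.

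**Working it through.** The plan gives no adverse-event rate, count or precision target, so there is no figure to reproduce. The check is a timeline, followed by a calculation for scale.

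**1. End of the window.** Sampling lasts 3 h and the bolus comes at 1.5 h (Section V.3). Planned observation after the bolus is 3 − 1.5 = 1.5 h. Planned routine follow-up after the visit is 0 h.

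**2. Washout.** The listed washouts run from more than 2 weeks (for example "Transdermal testosterone > 2 weeks") to more than 6 weeks (testosterone injections). Consent comes before all procedures, and washout comes before the visit.

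- Shortest: 2 × 7 × 24 = 336 h inside the window before the visit.
- Longest: 6 × 7 × 24 = 1008 h.
- The visit's share of washout plus visit is at most 3/339 = 0.9%, or 3/1011 = 0.3% for the longest.

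Weeks of washout are therefore covered. The uncovered part is the time from the end of the visit to the restart of medication. The documents do not state its length.

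**3. IV sites, side by side.**

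| Listed event | Position relative to the window |
|---|---|
| Pain, dizziness or fainting at placement or drawing | Inside |
| Irritation or bruising that shows early | Inside |
| Any event after the screening draw, before the visit ends | Inside |
| Infection or thrombosis first apparent after the visit | Outside |

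**4. Scale.** The documents call the IV-site risk small and give no number, so the rates here are assumptions. Let p be the per-participant risk of an event that starts after the visit, with participants independent. Then P(at least one) = 1 − (1 − p)^n. Section III gives n = 16 completers out of 32 enrolled. The n = 32 column is a ceiling that applies only if everyone enrolled had the visit.

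| Assumed p | n = 16 | Expected events, n = 16 | n = 32 |
|---|---|---|---|
| 1% | 1 − 0.99^16 = 15% | 0.16 | 27.5% |
| 5% | 1 − 0.95^16 = 56% | 0.8 | 80.6% |
| 10% | 1 − 0.90^16 = 81% | 1.6 | 96.6% |

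At p = 0.1% the n = 16 figure falls to 1 − 0.999^16 = 1.6%.

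**5. What a zero count would show.** The one-sided 95% upper bound with no events is 1 − 0.05^(1/n), which is 17.1% for n = 16 and 8.9% for n = 32. This limit comes from the sample size and would apply even with complete capture. Under the current rule it covers only events that start before procedures end.

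**The case against.** The strongest reply has four parts.

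**Washout is mostly covered.** A reader might infer that washout symptoms fall largely outside the window. The documents say otherwise: recording starts at consent and the washout precedes the visit. A symptom that begins during washout is recordable even if it persists. This part of the reply stands in full, and only symptoms that first arise after the visit and before restart are outside.

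**No onset times are given.** That infection or thrombosis would show after the visit is general reasoning, not something the protocol states. A reader might infer that these events will be under-counted, but the text supports only that they may be. The rates of 5% and 10% also sit uneasily with a risk described as small. This too stands, and it is why the 1% row and the 0.1% figure are shown.

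**Other routes exist.** Unanticipated problems, including related unanticipated serious events, go to the IRB within 5 working days or 7 calendar days of awareness, with no end date tied to the visit. The board receives serious-event reports as they occur and can ask for more. So the board is not shut off from everything late. But infection and thrombosis are listed risks and would not clearly count as unanticipated, and these routes work only if the team hears of the event. No contact is planned that would ensure it does. The gap that remains is mainly expected, non-serious, late-onset events.

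**Little depends on it.** The stated analysis is a paired comparison of mean LH, and no safety endpoint or safety table is planned. This is correct and limits the severity, but it does not remove the mismatch with the board's task.

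**Conclusion.** The point holds as a minor one. Recording ends with study procedures and no routine contact follows, so IV-site infection or thrombosis that first appears later, and washout symptoms that first arise between the visit and restart, may be missed.

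This rests on reading the undefined end of procedures as the end of the sampling visit. That is the natural reading but still an inference. It rests also on the general expectation that some IV-site harms appear late. The figures of 15%, 56% and 81% depend on assumed risks of 1%, 5% and 10% and show scale only. They assume that each event starts after the visit, and they do not estimate how many events would be lost. The 17.1% bound should not be read as a consequence of the window, since it reflects 16 participants.

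The LH comparison and its interpretation are unaffected.

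**What to change.** In Section IX (Adverse Event Documentation/Review), define the end of the window as one post-visit contact, by REDCap survey or phone call, at a single prespecified number of days after the visit. The investigators should choose that number and state it, since the documents give no onset times from which to derive it. The contact should ask about IV sites, general symptoms, and symptoms while washed-out medication is being resumed. Record onset dates so that in-visit and post-visit events can be reported separately. The same sentence should say when recording closes for participants who leave before the visit. List the contact in Section V so that the two sections agree.

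The cost is minor staff time for 16 to 32 contacts, in a system the study already uses, plus a few unrelated events recorded. No dose, schedule or treatment rule changes.
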